All Other irAEs	Persistent Grade 2 Grade 3	Withhold or discontinue based on the event e	Based on severity of AE administer corticosteroids	Ensure adequate evaluation to confirm etiology or exclude other
	Recurrent Grade 3 or Grade 4	Permanently discontinue		causes

AE(s)=adverse event(s); ALT= alanine aminotransferase; AST=aspartate aminotransferase; CTCAE=Common Terminology Criteria for Adverse Events; DRESS=Drug Rash with Eosinophilia and Systemic Symptom; GI=gastrointestinal; IO=immuno-oncology; ir=immune related; IV=intravenous; SJS=Stevens-Johnson Syndrome; T1DM=type 1 diabetes mellitus; TEN=Toxic Epidermal Necrolysis; ULN=upper limit of normal.

Note: Non-irAE will be managed as appropriate, following clinical practice recommendations.

- a AST/ALT: >3.0 to 5.0 x ULN if baseline normal; >3.0 to 5.0 x baseline, if baseline abnormal; bilirubin:>1.5 to 3.0 x ULN if baseline normal; >1.5 to 3.0 x baseline if baseline abnormal
- b AST/ALT: >5.0 to 20.0 x ULN, if baseline normal; >5.0 to 20.0 x baseline, if baseline abnormal; bilirubin:>3.0 to 10.0 x ULN if baseline normal; >3.0 to 10.0 x baseline if baseline abnormal
- c AST/ALT: >20.0 x ULN, if baseline normal; >20.0 x baseline, if baseline abnormal; bilirubin: >10.0 x ULN if baseline normal; >10.0 x baseline if baseline abnormal
- d The decision to withhold or permanently discontinue pembrolizumab is at the discretion of the investigator or treating physician. If control achieved or ≤ Grade 2, pembrolizumab may be resumed.
- e Events that require discontinuation include, but are not limited to: encephalitis and other clinically important irAEs.

Management of toxicities that are at least possibly related to entinostat, with toxicities graded by the Investigator according to the NCI CTCAE version 5.0 should be managed as follows:

Toxicity	Dose Modifications for Entinostat						
	Non-hematologic Toxicity						
Grade ≥ 3	Administer symptomatic remedies/start prophylaxis. Hold dose until recovery to Grade 1 or baseline under the following directions: If not recovered to Grade ≤ 2 within 1 week, permanently discontinue study drug.						
Grade ≤ 2	Administer symptomatic remedies/start prophylaxis.						
	Hematologic Toxicity						

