Grade ≥ 3 neutropenia, Grade ≥ 3 uncomplicated thrombocytopenia, or Grade 2 complicated thrombocytopenia	Administer symptomatic remedies/start prophylaxis. Hold dose until recovery to Grade 1 or study baseline. If not recovered by next scheduled dose, skip the dose. If recovered by next scheduled dose, resume study drug at prior dose.						

Entinostat may also be held for grade 2 treatment-related adverse events if deemed necessary by the site investigator. If treatment is held due to an adverse event clearly attributable to entinostat that is not listed in the table above and not immune-related, then the pembrolizumab may be continued (i.e. monotherapy). If the event is clearly attributable to pembrolizumab, then both agents will be held. If it is not possible to determine attribution, then both agents will be held. If more than one dose hold for the same event occurs, then the attributable drug should be permanently discontinued (ie, if entinostat is held twice for the same treatment-related adverse event, it will be permanently discontinued, but pembrolizumab may be continued). Doses of either drug should not be delayed, and any held doses will not be made up.

All protocol treatment will be permanently discontinued for any grade 4 non-hematologic event. Permanent discontinuation of all protocol related treatment will also occur for grade 3 non-hematologic adverse events such as myocardial infarction, poorly controlled arrhythmias, and adverse events requiring significant surgical intervention for management. Additionally, if grade >2 drug-related toxicity occurs that does not respond to supportive care within 48 hours and does not resolve to grade ≤ 1 within this timeframe, then the subject will be withdrawn from all protocol treatment and followed until symptom resolution.

Additionally, all protocol treatment will be permanently discontinued if patients have clinical disease progression or development of metastatic disease or require treatment with high dose steroids beyond 2 weeks.

Dose modifications/dose adjustments of either pembrolizumab or entinostat are not allowed.

Safety stopping rules for drug-related toxicity will dictate whether the trial should be halted if 2 subjects have their cystectomy (or maximal TURBT) delayed beyond the 10 weeks from the time of initiation of study therapy due to drug toxicity.

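### Section 5.4 gives two unranked instructions for entinostat-related toxicity of Grade 3 or higher that has neither responded nor settled by 48 hours: hold entinostat and decide later, or take the subject off both drugs

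*Combined protocol and SAP*

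**What the plan says.** All of the text at issue is in the current Section 5.4.

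- **Scope of the entinostat table.** It is introduced as "Management of toxicities that are at least possibly related to entinostat", graded by CTCAE version 5.0.
- **Non-hematologic row, Grade 3 or higher.** "Hold dose until recovery to Grade 1 or baseline under the following directions", followed by "If not recovered to Grade ≤ 2 within 1 week, permanently discontinue study drug".
- **Hematologic row** (Grade 3 or higher neutropenia, Grade 3 or higher uncomplicated thrombocytopenia, Grade 2 complicated thrombocytopenia). Hold to Grade 1 or study baseline, then: "If not recovered by next scheduled dose, skip the dose. If recovered by next scheduled dose, resume study drug at prior dose".
- **48-hour rule, in the free text below the table.** If drug-related toxicity above Grade 2 "does not respond to supportive care within 48 hours and does not resolve to grade" 1 or lower in the same period, "then the subject will be withdrawn from all protocol treatment".
- **Immediate-stop sentence, same paragraph.** Any Grade 4 non-hematologic event ends all treatment permanently. So do Grade 3 non-hematologic events such as myocardial infarction, poorly controlled arrhythmia, or events needing significant surgery.
- **Related provisions.** Held doses are not made up. If entinostat is held twice for the same event it is stopped, but pembrolizumab may go on.

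The 48-hour sentence exempts neither hematologic events, nor events attributed to entinostat alone, nor events that already have a row in the table. Nothing in Section 5.4 ranks the rules.

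**The concern.** For some events a site cannot follow both passages. One holds a single drug and postpones the decision; the other ends both drugs. The trial is now multicenter, and Section 11.5 requires conduct exactly as the protocol describes, so two sites could treat identical subjects differently and each cite Section 5.4.

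What is at stake is whether the subject receives the remaining entinostat doses and the Day 22 pembrolizumab. Because held doses are not made up, the difference is permanent. It also bears on the primary comparison: there are only 10 subjects per arm (Section 10.2), and Section 10.3 plans no table of doses received, so a reader of the results could not see how often the choice of rule had changed exposure.

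**Working it through.** The point rests on comparing text, and the plan has no figure of its own to reproduce here.

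**Step 1: the rules side by side.**

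| | Table, non-hematologic | Table, listed hematologic | 48-hour rule |
|---|---|---|---|
| Trigger | Grade 3 or higher, at least possibly entinostat-related | Grade 3 or higher neutropenia or uncomplicated thrombocytopenia; Grade 2 complicated thrombocytopenia | Above Grade 2, drug-related, no response **and** not Grade 1 or lower |
| Clock | 1 week | Next scheduled dose | 48 hours |
| Level to resume | Grade 1 or baseline | Grade 1 or baseline | Not applicable |
| Level to avoid a permanent stop | Grade 2 or lower at 1 week | None; the dose is skipped | Response, or Grade 1 or lower |
| What stops | Study drug, in a table of entinostat modifications | One entinostat dose | Both drugs |

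**Step 2: where they overlap.** The conflict needs all three of the following:

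- the event is at least possibly related to entinostat and has a row in the table;
- it is Grade 3 or higher;
- by 48 hours it has neither responded to supportive measures nor come down to Grade 1 or lower.

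An event that has responded by 48 hours but is still above Grade 1 falls under the table alone. So does Grade 2 complicated thrombocytopenia, which is not above Grade 2. Grade 4 non-hematologic events and the named kinds of Grade 3 event go to the immediate-stop sentence. That is a second mismatch, because the table's non-hematologic row tells sites to hold for Grade 3 or higher without excepting them.

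**Step 3: doses under each rule.** Inputs are the Arm 2 schedule in Section 5.2 (entinostat Days 1, 8 and 15; pembrolizumab Days 1 and 22) and the rule that held doses are not made up. The event is Grade 3 neutropenia related to entinostat.

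| Course | Table | 48-hour rule |
|---|---|---|
| Starts Day 3, no response by Day 5, Grade 1 on Day 7 | Entinostat Days 1, 8, 15 = 3; pembrolizumab Days 1, 22 = up to 2 | Off on Day 5: entinostat 1, pembrolizumab 1 |
| Starts Day 9, no response by Day 11, Grade 1 on Day 14 | 3 and up to 2 | Off on Day 11: 2 and 1 |
| Starts Day 16, no response by Day 18, Grade 1 on Day 20 | 3 and up to 2 | Off on Day 18: 3 and 1 |

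The entinostat difference is 3 − 1 = 2, 3 − 2 = 1 or 3 − 3 = 0 doses, by time of onset. The pembrolizumab difference is up to 2 − 1 = 1 dose in each case. A Grade 3 non-hematologic event with the same course gives the same split, unless it is of a kind named in the immediate-stop sentence: recovery takes 4 or 5 days, inside the 1-week limit.

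**Step 4: can the 48-hour limit be observed?** During treatment the Time and Events Table schedules hematology, chemistry and toxicity assessment on Days 1, 8, 15 and 22, each ±1 day. Consecutive visits are therefore at least 7 − 2 = 5 days (120 hours) apart, so the 48-hour mark will usually fall between visits. Appendix F obliges the investigator to arrange further measurements as medically indicated, so a check is possible. But Section 5.4 does not say when it is made or what counts as a response.

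**The case against.** The strongest reply is that the 48-hour paragraph opens as an addition and can be read as a stop rule laid over the hold rules, so that the stricter provision governs. That is a fair reading, but the protocol does not state it, and the clause letting pembrolizumab continue after repeated entinostat holds points the other way. Nor would precedence empty either rule. If the 48-hour rule came first, the table would still govern events that respond or resolve in time and Grade 2 complicated thrombocytopenia. A precedence sentence is therefore a workable repair.

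The reply is right to limit the point in other ways. A reader might infer:

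- **That every Grade 3 or higher event lasting between 2 and 7 days is handled in opposite ways.** It is not. The 48-hour condition has two parts, and a response within 48 hours takes the event out of it.
- **That one rule keeps giving entinostat through unresolved severe toxicity.** It does not. The table holds entinostat to Grade 1 or baseline, so the rules part over entinostat after recovery and over Day 22 pembrolizumab.
- **That the conflict removes pembrolizumab mainly in Arm 2 and so biases the contrast.** The table matters only in Arm 2, but the 48-hour rule reaches drug-related toxicity in both arms. Section 5.4 also holds both agents when attribution cannot be determined, so pembrolizumab can be lost in Arm 2 for other reasons.

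The events may also be rare. Section 1.1 reports neutropenia and anemia only above the doses used here, and Section 6.2.6 does not expect adverse events to be an issue with three doses. That bears on frequency, not on whether the text is consistent.

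**Conclusion.** The contradiction stands within the limits of Step 2. For those events Section 5.4 both holds entinostat with a later decision and ends both drugs, without ranking the two. In the worked cases the choice is worth up to 2 entinostat doses and up to 1 pembrolizumab dose for the subject concerned. The immediate-stop sentence has a related mismatch with the table.

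The dose counts assume that the table's study drug means entinostat, and that nothing else prevents the Day 22 infusion; hence up to 2.

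The effect on the primary comparison cannot be sized. A reader might turn the lost doses into a loss of power, but that needs the number of subjects affected and the effect of each lost dose on the T cell signature. The documents give neither for this schedule, so any power figure would be pure assumption and none is offered. The case for acting is that sites cannot comply with both passages and that the repair is cheap. No view is taken on which clinical limit is right.

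**What to change.** 1. Reconcile the 48-hour sentence with both rows of the entinostat table, either by stating which prevails or by giving each class of toxicity one time limit, one recovery grade and one scope (entinostat only, or all treatment). The investigators choose the limits.
2. In the same edit, reconcile the immediate-stop sentence for Grade 4 and selected Grade 3 non-hematologic events with the table's Grade 3 or higher row.
3. If the chosen limit is shorter than the interval between scheduled visits, state how and when response and recovery are assessed.
4. Add to Section 10.3 a table, by arm, of pembrolizumab and entinostat doses received.

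The cost is wording in the next amendment and one descriptive table. Sample size and the primary analysis are unchanged.

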Blood and tumor will then be collected from each subject at the time of post-treatment surgery (cystectomy or maximal TURBT (within 10 weeks after initiation of protocol therapy)) [2, 3]. We do not anticipate delays in surgery due to the planned schedule of the preoperative treatment administration for the purposes of this study and based on the phase II ENCORE 601 trial (pembrolizumab and entinostat in melanoma) which reported an acceptable safety profile [4-6]. Phase I data identified grade 1/2 fatigue as the most common entinostat-related toxicity, with neutropenia and anemia only occurring at doses exceeding those proposed for this study. Safety stopping rules for drug-related toxicity will dictate whether the trial should be halted if subjects are experiencing drug-related toxicity that delays or interferes with standard of care procedures.

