2.2 Secondary Objectives

- 2.2.1 To characterize the changes in neoantigen expression and T cell receptor (TCR) clonality in blood and tumor samples after treatment with pembrolizumab alone and the combination of pembrolizumab and entinostat.
- 2.2.2 To evaluate the changes in STAT and NF-κB gene signatures and histone acetylation (H3K9Ac, H3K27Ac, and others) levels after combination treatment with pembrolizumab and entinostat as compared to pembrolizumab alone (subset of subjects with frozen pre- and post-treatment tumor tissue available).
- 2.2.3 To document safety, tolerability, and feasibility of preoperative administration of pembrolizumab with and without entinostat in cisplatin-ineligible MIBC patients prior to scheduled surgical resection, and to document safety, tolerability and feasibility of pembrolizumab with and without entinostat prior to trimodality therapy in MIBC patients (National Cancer Institute Common Terminology for Adverse Events [NCI-CTCAE v5.0]).
- 2.2.4 To define the pathologic response rate (<pT2) and pathologic complete response rate (pT0) after treatment with pembrolizumab alone and the combination of pembrolizumab and entinostat in cisplatin-ineligible subjects undergoing radical cystectomy
- 2.2.5 To estimate the clinical complete response rate (cT0) after treatment with pembrolizumab alone and the combination of pembrolizumab and entinostat in patients undergoing maximal TURBT prior to chemoradiation
- 2.2.6 To estimate the event free survival (EFS) after treatment with pembrolizumab alone and the combination of pembrolizumab and entinostat in patients with MIBC

- 2.2.7 To estimate overall survival (OS) after treatment with pembrolizumab alone and the combination of pembrolizumab and entinostat in patients with MIBC
- 2.3 Exploratory Objectives

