8.2 Post-Treatment Surgery

Post-treatment surgery (either cystectomy or maximal TURBT for trimodality patients) should occur within 10 weeks of the initiation of study therapy. For cystectomy subjects, the surgery with curative intent will occur as per routine clinical standard of care and will be performed at the discretion of the surgeon. For subjects undergoing trimodality therapy, maximal TURBT should occur within 10 weeks of initiation of study therapy, followed by initiation of standard of care concurrent chemotherapy and radiation.

Tissue acquisition: A sample of tumor tissue from the post-treatment surgery will be preserved for correlative studies. A sample of lymph node tissue from the lymph node dissection, if available, and normal tissue from the cystectomy specimen will be preserved for correlative studies from all cystectomy subjects. These tissues will be preserved in consultation with surgical pathology, and tissue released for correlative studies post pathological review. Note: Subjects who do not complete clinical trial treatment for whatever reason other than withdrawal from the study, but still undergo surgery, will be requested to participate in correlative studies.

Blood sample for correlative studies: blood will be collected in ACD tubes (see Study Laboratory Manual for details).

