8.2.1 Post-Surgery Visit

This visit should be scheduled 4-8 weeks after cystectomy, or 2-4 weeks after maximal TURBT for trimodality subjects. This visit should occur prior to initiation of subsequent standard of care chemotherapy and radiation in trimodality subjects. Initiation of chemotherapy and radiation should occur per standard of care after maximal TURBT. Serious adverse events (SAEs) related to protocol-mandated treatment or any grade of Events of Clinical Interest (see section 9.4.2.2) that occur within 90 days of pembrolizumab administration must be recorded.

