10.3 Data Analysis Plans

The change in T cell gene signature expression will be calculated for each group (pembrolizumab + entinostat compared to pembrolizumab alone) and compared between groups using a two group t-test. Similar analyses will be done for all gene signatures.

Appropriate descriptive statistics, including median, interquartile range, means, and 95% confidence intervals, will be calculated and reported for all lab values.

The analysis of the toxicity and safety will be based on the frequency of adverse events and their severity. Worst toxicity grades per subject will be tabulated for adverse events and laboratory measurements by using the National Cancer Institute- Common Terminology Criteria for Adverse Events (NCI-CTCAE version 5.0) and will be reported in the form of frequency tables. If 2 subjects have their surgical resection delayed beyond the 10 weeks from the time of initiation of study therapy due to protocol treatment-related adverse events, further enrollment to the study will be halted. Based on the nature and severity of

LCCC 1827 PI: [name], MPH Amendment 6 CONFIDENTIAL UNIVERSITY OF NORTH CAROLINA January 9, 2025

the toxicities observed, consideration will be made to amend the study (if risk of toxicity is felt to be mitigated by protocol amendment) vs terminating the study. If 4 or more patients are delayed due to protocol treatment-related adverse events, then the study will be terminated.

For subjects that undergo cystectomy, the proportion of patients who have a pathologic response to <pT2 will be reported along with a 95% confidence interval. Similarly, the proportion of patients who have a clinical complete response (cT0) will be reported separately for those undergoing cystectomy and trimodality therapy. Patients who progress prior to surgery (unlikely) or do not have surgery will still be included in this estimate and will be considered to have not been downstaged. The Kaplan Meier method will be used to estimate median times, along with 95% confidence intervals, for the secondary objectives of EFS and OS, as defined in Section 3.2.6 and 3.2.7.

Results gathered on these subjects will be highly valuable in providing information that can be used to inform power and sample size considerations for future investigations.

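### For trimodality subjects the pre-specified halt counts a late TURBT but not chemoradiation that study-drug toxicity postpones or prevents, although the synopsis gives the stopping rules a wider purpose

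*Combined protocol and SAP*

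**What the plan says.** Section 1.1 states the purpose: the rules decide whether to halt "if subjects are experiencing drug-related toxicity that delays or interferes with standard of care procedures".

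Two sections put that purpose into operation.
- Section 5.4 considers a halt if "2 subjects have their cystectomy (or maximal TURBT) delayed beyond the 10 weeks from the time of initiation of study therapy" because of drug toxicity.
- Section 10.3 begins "If 2 subjects have their surgical resection delayed beyond the 10 weeks from the time of initiation of study therapy", requires that protocol treatment-related adverse events be the cause, and then stops enrolment. It adds: "If 4 or more patients are delayed due to protocol treatment-related adverse events, then the study will be terminated".

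Inclusion criterion 4.1.8 defines trimodality therapy as repeat TURBT and then concurrent chemoradiation, for subjects who are not candidates for cystectomy or who refuse it. Section 8.2 says that "maximal TURBT should occur within 10 weeks of initiation of study therapy, followed by initiation of standard of care concurrent chemotherapy and radiation". Section 8.2.1 places the post-surgery visit 2-4 weeks after TURBT and says "This visit should occur prior to initiation of subsequent standard of care chemotherapy and radiation in trimodality subjects". It times chemoradiation by standard of care and gives no window. Secondary objective 2.2.3 is to "document safety, tolerability and feasibility of pembrolizumab with and without entinostat prior to trimodality therapy in MIBC patients".

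**The concern.** For a cystectomy subject, the milestone that the rule watches is the definitive treatment. For a trimodality subject it is only the first part. A subject can have TURBT inside 10 weeks and then have treatment-related toxicity that postpones or rules out chemoradiation. That subject adds nothing to the count of 2, although this is the kind of interference that 1.1 describes. These subjects are by definition not going to cystectomy, so what is at stake is the remainder of their curative-intent treatment.

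The two operative sections also differ from each other: 5.4 names maximal TURBT and 10.3 does not.

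**Working it through.** **Plan's own figure.** The documents give no operating characteristics for the halting rule, so there is none to reproduce. The check is first textual and then an illustration.

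**Step 1: the texts side by side.**

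| Place | What is covered | Count or clock |
|---|---|---|
| 1.1 | Toxicity affecting standard-of-care procedures in general | None given |
| 5.4 | Cystectomy or maximal TURBT | 2 subjects, 10 weeks |
| 10.3, halt | Surgical resection | 2 subjects, 10 weeks |
| 10.3, termination | Patients delayed; no procedure named | 4 or more |
| 8.2, 8.2.1 | Chemoradiation, called standard of care | No limit; not a halting event |

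Section 1.1 has no count and no clock, so it cannot trigger anything itself. The termination sentence follows the one on surgical resection, so its natural reading is surgical delay.

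**Step 2: when such toxicity could appear.** Inputs are the last pembrolizumab dose on Day 22 (5.2), TURBT by week 10 (8.2), the visit 2-4 weeks later (8.2.1), and 90-day recording of SAEs caused by a protocol-mandated intervention (9.2.1). Day 71 is the latest permitted TURBT, not the expected one.
- TURBT at 10 weeks: Day 1 + 70 = Day 71.
- Post-surgery visit: Day 71 + 14 to 28 = Day 85-99.
- Time since last pembrolizumab: 85 − 22 = 63 to 99 − 22 = 77 days.
- End of the 90-day window: 22 + 90 = Day 112.
- End of the 30-day documentation of non-serious events (9.3): 22 + 30 = Day 52.

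Footnote 12 of the Time and Events Table drops the pre-surgery history and toxicity assessment for TURBT subjects, though safety labs remain. After Day 22, their next scheduled toxicity assessment is therefore the post-surgery visit. Toxicity first found there, after an on-time TURBT, cannot count under 5.4.

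**Step 3: size, by assumption.** Let k be the number of trimodality subjects and q the chance that study-drug toxicity postpones or prevents chemoradiation after an on-time TURBT. Neither is in the documents. Section 10.2 sets N = 20, with a tissue-adequacy review after 5 trimodality subjects and no cap.

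P(at least 2) = 1 − (1 − q)^k − k·q·(1 − q)^(k−1)

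| k | q | Calculation | P(at least 2) | Counted by written rule |
|---|---|---|---|---|
| 5 | 10% | 1 − 0.590 − 0.328 | 8% | 0 |
| 5 | 20% | 1 − 0.328 − 0.410 | 26% | 0 |
| 10 | 10% | 1 − 0.349 − 0.387 | 26% | 0 |
| 10 | 20% | 1 − 0.107 − 0.268 | 62% | 0 |

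**Step 4: effect on the chance of a halt.** Assume also that 5% of all 20 subjects have a counted surgical delay. As written, P(at least 2 of 20) = 1 − 0.95^20 − 20·0.05·0.95^19 = 1 − 0.358 − 0.377 = 26%.

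If chemoradiation events counted, each trimodality subject's chance would be 0.05 + 0.95q, which is 0.145 at q = 10% and 0.24 at q = 20%. Combining 20 − k cystectomy subjects with k trimodality subjects gives 44% and 60% for k = 5, and 60% and 82% for k = 10. The chance of 4 or more moves from 1.6% to 5.3% and 11.5% (k = 5), or to 12.1% and 32.6% (k = 10).

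**The case against.** **Oversight exists outside the rule.** Section 9.6 requires continuous safety monitoring by the principal investigator, team meetings, and DSMC review quarterly to annually. Toxicity is assessed before chemoradiation, and SAEs go to the entinostat supplier within 24 hours (9.4.3). This stands. What is missing is the automatic count. Cystectomy subjects have the same oversight and a numerical rule as well.

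**The milestone has a rationale.** Section 1.2 describes the trimodality window as ending at the repeat TURBT, which is the only trimodality step with a protocol deadline. Chemoradiation regimens are not mandated (4.1.8), and with no window a postponement has no definition. This stands in part: TURBT is a sensible milestone, and toxicity that pushes it past 10 weeks already counts under 5.4. But cystectomy is also routine care under 8.2 and the rule covers it, and 1.1 does not stop at the window.

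**The termination sentence names no procedure.** This is correct. Its exclusion of chemoradiation is the natural reading, not an explicit one.

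**The size is assumed.** This too is correct. The review in 10.2 could also restrict accrual to cystectomy after 5 trimodality subjects, which is why both k = 5 and k = 10 are shown.

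**Conclusion.** The rule in 5.4 and 10.3 is narrower than the purpose in 1.1. In trimodality subjects, toxicity that spares TURBT but postpones or prevents chemoradiation falls outside the halt at 2. This rests on the text alone. The probabilities only illustrate it and depend on the assumed k and q, with subjects treated as independent.

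A reader might infer three stronger things that the documents do not support.
- That such toxicity could recur throughout accrual with no review at all. Section 9.6 provides review; acting on it is discretionary.
- That the feasibility conclusion under 2.2.3 would rest only on TURBT timing. Endpoint 3.2.3 and section 10.3 also report CTCAE toxicity, although neither captures whether chemoradiation started.
- That 5.5 already ensures that the chemoradiation date is captured. It mentions initiation of chemoradiation as a limit for recording concomitant medications, but the recording runs to 4 weeks after the last dose (22 + 28 = Day 50). The Time and Events Table ends that row at surgery and has no row for the chemoradiation start.

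**What to change.** Reconcile 1.1, 5.4, 8.2, 8.2.1 and 10.3. Use the same wording for the rule in 5.4 and 10.3, naming the procedures for each population. State that a trimodality subject whose chemoradiation is postponed beyond a limit the sponsor sets, or is not started, because of protocol treatment-related adverse events counts toward the same thresholds of 2 and 4. No time limit is proposed here.

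Record the chemoradiation start date, or the reason it was not started with attribution, when it becomes known after the post-surgery visit. Waiting for the 6-monthly follow-up would be too slow for a halting rule when accrual lasts two years. Report the item under 2.2.3. Because non-serious events are documented for only 30 days after treatment, the attribution should be part of the entry.

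The cost is revised wording, one eCRF item and a higher chance of a halt. The size of that increase depends on how often the event occurs: there is none if it never occurs, and Step 4 shows the increase under the assumed rates.
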